5.2 Inclusion criteria

Subjects must meet all the following inclusion criteria to be eligible for enrollment into the study:

- 1. Subjects between 18-75 years of age (inclusive), male or female, at the time of informed consent
- 2. Moderate to severe atopic dermatitis, as determined by all of the following:
 - Have a clinical diagnosis of AD for at least 1 year before Visit 1 (Chinese Criteria of AD refer to Appendix 1)
 - \circ EASI \geq 12, BSA \geq 10%, and IGA \geq 3 at the Screening and Baseline Visits
 - o In the judgment of the investigator, subjects who have inadequate response and/or cannot be tolerable, to one or more of the below treatments for at least 4 weeks
 - Topical therapy (topical corticosteroids and/or topical calcineurin inhibitors)
 - Systemic steroids and/or phototherapy

- Cyclosporine and/or other immunomodulators (e.g., methotrexate, mycophenolate mofetil, and azathioprine, etc.)
- 3. Capable of providing a signed and dated informed consent form indicating the subject has been informed of all pertinent aspect of the study
- 4. All women of childbearing potential and all men must be willing to use at least one highly effective method of contraception from signing of informed consent, throughout the duration of the study, and for 1 month after last dose of study medication: (refer to Section 5.4 for further details on contraception requirements for this study)
 - o Male subjects with a female partner of childbearing potential must be willing to use condom in addition to a highly effective contraceptive method.
- 5. Subjects who are willing and able to comply with the scheduled visits and treatment plan, laboratory testing and other study procedure
- 6. Subjects receiving non-prohibited concomitant medications for any reason must maintain a stable dosing regimen, defined as no administration of a new drug or no change in dose within 7 days or 5 half-lives (whichever is longer) prior to the first dose of study drug

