Appendix 1 Atopic Dermatitis Diagnosis -Chinese Criteria

In 2016, Profession Zhang et al. reported Chinese Criterial for atopic dermatitis diagnosis. There are 3 criteria, subjects who meet the first criterion together with one of the 2nd or 3rd criterion can be diagnosed as atopic dermatitis:

- 1. Symmetrical eczema (dermatitis) for more than 6 months
- 2. Personal and/or family history of atopic diseases
- 3. Elevated total serum Ig E level and/or positive allergen-specific Ig E and/or eosinophilia

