3.2.2.2 Efficacy endpoints

- The percentage change in EASI score from baseline at weeks 1, 4, 8, and 12.
- The percentage of subjects who achieve IGA response at weeks 1, 4, and 8.
- The percentage of subjects whose EASI scores improve by $\geq 50\%$, 75%, and 90% (EASI50, EASI75, EASI90) from baseline at weeks 1, 4, 8, and 12.
- Changes in scoring atopic dermatitis (SCORAD) from baseline at weeks 1, 4, 8, and 12.
- The percentage of subjects whose SCORAD improve by $\geq 50\%$, 75%, and 90% (SCORAD50, SCORAD75, SCORAD90) from baseline at weeks 1, 4, 8, and 12.
- The percentage change in Pruritus Numerical Rating Scale (NRS) from baseline at weeks 1, 4, 8, and 12.
- The percentage of subjects whose NRS improve by ≥ 3 points from baseline (NRS-3) at weeks 1, 4, 8, and 12.
- Changes in Dermatology Life Quality Index (DLQI) from baseline at weeks 1, 4, 8, and 12.
- Changes in biomarker immunoglobulin E (IgE) from baseline at weeks 1, 4, 8, and 12.
- Changes in absolute eosinophil count from baseline at weeks 1, 4, 8, and 12.

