11.1 BASELINE DEFINITION AND CHANGE FROM BASELINE

Unless otherwise specified, the baseline value for a parameter of interest is the latest non-missing value prior to date of the first administration of study drug.

Change from baseline and percentage from baseline will be derived as follows:

- Change from baseline = the post-baseline value - the baseline value of a parameter of interest for a subject.
- Percentage change from baseline = (post-baseline value - the baseline value)/ baseline value of a parameter of interest for a subject.

If either the baseline or the post-baseline value is missing, then the change or percentage change will be set to missing.

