The number and percentage of subjects achieving EAS50, EAS75, and EAS90 will also be summarized for each treatment group at each efficacy assessment visit.

14.3.4 Change from baseline in SCORAD at Week 1, Week 4, Week 8, and Week 12

The SCORAD score integrates the observational assessment of physicians and patients. The scoring scale consists of three major sections: the objective signs section includes lesion area and lesion severity, and the subjective symptoms include the degree of itching and sleep effects. SCORAD scores range from 0 to 103.

SCORAD quantitative results will be analyzed using the same MMRM method as EASI.

The SCORAD scores and change from baseline at each assessment visit will be summarized, and the scores of each objective sign sections (lesion area, lesion severity) and the subjective symptom (pruritus, impact on sleep) will be summarized using statistics including mean, standard deviation and 90% confidence interval. A line graph will be used to graphically display the least squares mean of change from baseline in SCORAD score for each treatment assessment visit (including five scales: Total Score, A Lesion Area, B Lesion Severity, C Pruritus and sleeplessness).

14.3.5 Percentage of subjects With $\geq 50\%$, 75% , and 90% SCORAD improvement from baseline (SCORAD50, SCORAD75, SCORAD90) at Weeks 1, 4, 8, and 12

Percentage of SCORAD change from baseline will also be derived as a dichotomous result based on the following three criteria: $\geq 50\%$ (SCORAD50), $\geq 75\%$ (SCORAD75), and $\geq 90\%$ (SCORAD90). For each derived dichotomous SCORAD result, the comparison between 4 mg QD and 8 mg QD versus placebo will be performed using method of normal approximation to binomial or Fisher's exact test, respectively, according to actual data distribution.

The number and percentage of subjects achieving SCORAD50, SCORAD75 and SCORAD90 will also be reported.

14.3.6 Percent of pruritus numerical Rating scale (NRS) change from baseline at Weeks 1, 4, 8, and 12

At each visit, the degree of pruritus/scratching is assessed by the subject on an 11-grade rating scale from 0 (no pruritus/scratching) - 10 (severe pruritus/scratching) for the first 24 hour of the visit.

The NRS quantitative results will be analyzed using the same MMRM method as for EASI.

The NRS score and change from baseline at each efficacy assessment visit will be summarized by treatment and mean, standard deviation and 90% confidence interval will be provided.

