14.3.7 Percentage of subjects achieving pruritus NRS improvement ≥ 3 from baseline in at Weeks 1, 4, 8, and 12

Percentage of NRS change from baseline will also be derived into two categories: ≥ 3 points and < 3 points. Dichotomized NRS results will be compared between 4 mg QD and 8 mg QD versus placebo groups using method of normal approximation to binomial or Fisher's exact test, respectively, according to actual data distribution, noting that the comparison of NRS differences will only be performed in the population with baseline NRS score ≥ 3 .

The number and percentage of NRS will also be reported as follows: 0, 1-3, 4-6, 7-9 and 10 points for 5 grades.

14.3.8 Change from baseline in dermatology life quality index (DLQI) at Weeks 1, 4, 8, and 12

The DLQI is a dermatology-related questionnaire that allows subjects to assess the impact of skin disease on quality of life through 10 questions with total score ranging from 0 to 30.

The rules for scoring the 10 questions are as follows:

- Not at all: 0 points (Item 7 Question: No (Not at all), 0 points);
- A little: 1 point (question 7: no (a little), 1 point);
- Many: 2 points (question 7: No (many), 2 points);
- Very much: 3 points (question 7: Yes, 3 points).

Change from baseline in DLQI will be analyzed using the same MMRM model as the EASI.

The DLQI score and change from baseline at each treatment visit will be summarized using statistics including mean, standard deviation, and 90% confidence interval.

14.3.9 Change from baseline in biomarker IgE at Weeks 1, 4, 8 and 12

Atopic dermatitis is divided into endogenous and exogenous types. Patients with exogenous AD usually present with elevated serum total IgE.

Change from baseline in IgE will be analyzed using the same MMRM model as the EASI.

IgE and change from baseline will be summarized by treatment group at each efficacy assessment visit using statistics including mean, standard deviation and 90% confidence interval.

14.3.10 Change in absolute eosinophil count from baseline at Weeks 1, 4, 8, and 12

The change from baseline in absolute eosinophil count will be analyzed using the same MMRM model as described for the EASI.

Absolute eosinophil counts and changes from baseline will be summarized by treatment group at each efficacy assessment visit using statistics including mean, standard deviation, and 90% confidence intervals.

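### Pruritus NRS is modelled as percentage change from baseline although entry sets no minimum itch score: baseline 0 has no value and no rule, and baselines of 1 or 2 can cost precision

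*SAP*

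**What the plan says.** **Entry.** Protocol 5.2 requires EASI of at least 12, BSA of at least 10% and IGA of at least 3 "at the Screening and Baseline Visits". No inclusion or exclusion criterion names the pruritus NRS. The diagnostic criteria in Protocol Appendix 1, which begin with "Symmetrical eczema (dermatitis) for more than 6 months", do not include itch.

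**Endpoint.** SAP 3.2.2.2 lists "The percentage change in Pruritus Numerical Rating Scale (NRS) from baseline at weeks 1, 4, 8, and 12" as a secondary endpoint. Protocol 9.2.2 also names percent change and assigns it to the MMRM.

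**Derivation.** SAP 11.1: "Percentage change from baseline = (post-baseline value - the baseline value)/ baseline value of a parameter of interest for a subject". The same section sets the result to missing if either value is missing. It does not mention a baseline of zero. SAP 14.3 does not impute missing continuous endpoints.

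**Model.** SAP 14.3.6: "The NRS quantitative results will be analyzed using the same MMRM method as for EASI". No baseline restriction is attached, and the default set is the FAS. The reference code in SAP 14.3.2, which NRS inherits, describes its response as change from baseline in EASI, while the text of that section says percentage change.

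**Neighbouring endpoint.** SAP 14.3.7, on improvement of at least 3 points, adds that the "comparison of NRS differences will only be performed in the population with baseline NRS score" of at least 3.

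**The concern.** The MMRM was written for EASI, whose denominator is protected at entry: at a baseline of 12 or more, one EASI point is at most 100/12 = 8%. The NRS runs from 0 to 10 with no entry floor, so its denominator can be 0, 1 or 2.

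Two things follow. A subject at baseline 0 has no percentage change at any visit and cannot enter the model. The SAP does not say so; it follows from the formula and the no-imputation rule. This is exclusion from one analysis, not study withdrawal. A subject at baseline 1 or 2 stays in, but on a scale where ordinary day-to-day variation becomes hundreds of percent. Baseline as a covariate shifts the fitted mean. It does not remove the unequal variance or the leverage of such values.

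At stake is the precision of one patient-reported secondary endpoint, tested at two-sided 0.10 (SAP 8). The plan has no modelled fallback for it: absolute NRS change is only summarised descriptively, and the sensitivity analyses in SAP 14.4 cover IGA and EASI, not NRS.

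**Working it through.** **Plan's own figure.** There is none to reproduce. The documents give no SD, effect size, power or baseline distribution for the NRS.

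**Inputs from the documents.** Scale 0-10 (SAP 14.3.6); formula (SAP 11.1); 35 per arm (SAP 6; the protocol plans 44); two-sided 0.10 (SAP 8).

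**Step 1: range of the ratio.** Percentage change = 100 × (post − baseline)/baseline. One point is worth 100/b percent at baseline b, and the largest worsening is 100 × (10 − b)/b.

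| Baseline b | One point | Largest worsening |
|---|---|---|
| 0 | undefined | undefined |
| 1 | 100% | +900% |
| 2 | 50% | +400% |
| 3 | 33% | +233% |
| 7 | 14% | +43% |
| 10 | 10% | 0% |

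Improvement is bounded at −100% for every b of 1 or more, so extreme values occur on one side only.

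**Step 2: one subject.** Assume 34 placebo subjects with mean −20% and SD 35, plus one who goes from NRS 1 to 6 (+500%).

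- Arm mean: (34 × (−20) + 500)/35 = −5.1, a shift of 14.9 points.
- Arm sum of squares: 33 × 35² + (34/35) × 520² = 40,425 + 262,674 = 303,099. SD = √(303,099/34) = 94.4.
- SE of the difference from an arm of 35 with SD 35: before, √(2 × 35²/35) = 8.4; after, √((94.4² + 35²)/35) = 17.0.

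For contrast, a subject going from 8 to 10 (+25%) contributes 25/35 = 0.7 points to the arm mean.

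**Step 3: illustrative power.** All of the following are assumptions:

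- Most baselines are about 7 (SD 1.5, rounded, kept within 3-10). A share q is split equally over 0, 1 and 2.
- Change SD is 2 points. Mean change is −1 on placebo and −2.5 on active at baseline 3 or more, with none assumed at 0-2. Scores are kept within 0-10.
- One active arm is compared with placebo, 35 per arm, at a single visit by ANCOVA with baseline as covariate, two-sided 0.10, 5,000 runs per row.

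| Share at NRS 0-2 | Excluded (baseline 0) | Share of variation from baseline 1-2 | Power, % change | Power, absolute change |
|---|---|---|---|---|
| 0% | 0% | 0% | 90% | 92% |
| 3% | 1.0% | 17% | 80% | 90% |
| 5% | 1.7% | 27% | 76% | 89% |
| 10% | 3.3% | 44% | 62% | 86% |
| 15% | 5.1% | 56% | 53% | 84% |
| 20% | 6.7% | 65% | 42% | 79% |

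A repeat run at 3%, 6% and 10% gave about 81%, 72% and 62% for percentage change, with absolute change at 86-91%.

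**Step 4: dependence on fluctuation.** A second ANCOVA simulation of the same size, with its own illustrative assumptions, gave 77%, 66% and 56% at shares of 3%, 6% and 10% with a change SD of 2 points. With an SD of 1 point it gave 84%, 77% and 69%. Only the gap carries over to the table above: less fluctuation means a smaller loss.

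**Step 5: type I error.** With no true difference, rejection stayed at 9-10% for shares of 0-10%, against the nominal 10%.

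**The case against.** **Low baselines may be rare.** Subjects must have moderate to severe disease and inadequate response or intolerance to earlier treatment, and they wash out topical and systemic therapy. The protocol's background describes severe pruritus as characteristic. This stands: nothing in the documents supports a particular share below 3. It does not make the share zero, because the NRS is a single 24-hour rating and oral antihistamines are permitted (Protocol 6.6.1).

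**Other itch results are planned.** SAP 14.3.6 summarises absolute NRS change with mean, SD and 90% CI. SAP 14.3.7 adds a five-grade distribution and the responder comparison, and SCORAD includes itch. A distorted percentage mean would be visible beside these. This stands in part: none of them is a modelled comparison of absolute NRS change between arms.

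**The model may already be absolute change.** Read literally, the reference code suggests so. The endpoint lists and the heading of 14.3.6 say percentage, so the ambiguity is a further item to correct and does not answer the point.

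**Section 14.3.7.** A reader might infer that its baseline restriction shows the SAP recognising the denominator problem and then overlooking it one section earlier. The documents do not support that. A 3-point improvement is impossible from a baseline below 3, which is reason enough for the restriction. The different populations follow from the responder definition. The restriction simply does not reach 14.3.6.

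**Conclusion.** The gap is real and its consequence is limited. Baseline 0 has no computable value and no stated rule. Baselines of 1 or 2 can inflate the variance and lower power for percentage change in NRS. On the assumptions shown, power goes from about 90% to about 81%, 72% and 62% if 3%, 6% and 10% of subjects enter at NRS 0-2. The loss shrinks if those subjects fluctuate less and is negligible if almost nobody enters that low. These figures come from a single-visit ANCOVA, not the planned MMRM, and both the low-baseline share and the fluctuation are assumed.

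Two stronger readings do not hold. A reader might infer that a few low-itch subjects will dominate or decide the itch result. The documents give no baseline NRS distribution, and in the table above subjects at baseline 1-2 supply more than half the variation only when roughly 12-15% or more enter at 0-2. A reader might also fear a spurious positive finding, but type I error stays near its nominal 10%. The primary IGA analysis is not affected.

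**What to change.** Before unblinding, amend SAP 14.3.6 as follows.

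1. Add an MMRM of absolute NRS change (points) in the full FAS, with baseline NRS as covariate. Every baseline score from 0 to 10 can then enter a modelled comparison.
2. State that the percentage-change MMRM is run in subjects with baseline NRS of at least 3. This removes zero denominators and caps worsening at +233%. Because baseline precedes treatment, the randomised comparison is kept. If the sponsor prefers to keep the full FAS for this endpoint, then at the least state how baseline 0 is handled and report the restricted analysis as a sensitivity analysis.
3. Correct the reference code in SAP 14.3.2 so that the response variable for the percentage-change endpoints (EASI and NRS) is percentage change.

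The cost is a few lines of SAP text and one extra table. The percentage-change analysis loses the subjects with baseline NRS below 3, probably few, who remain in the absolute-change analysis. The same rule chosen after unblinding would look data-driven.

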14.4 SENSITIVITY ANALYSES

14.4.1 Statistical analysis methods

The primary efficacy endpoint of IGA response at Week 12 specified in Section 14.2 will be tested based on the full analysis set (FAS) using Fisher's exact test together with Exact Unconditional 90% confidence interval of difference between active groups versus placebo group. The 90% confidence interval of IGA response rate at Week 12 based on Clopper-Pearson method will also be reported for each treatment group.

Referenced SAS code:

```
PROC FREQ DATA = adam.adeff;  
  TABLE treat*aval/CHISQ RISKDIFF ALPHA = 0.1;  
  EXACT RISKDIFF (METHOD = SCORE);  
  RUN;
```

14.4.2 Analysis set

Sensitivity analyses of the primary efficacy endpoint (IGA response at Week 12), EASI50, EASI75, EASI90, and EASI quantitative results at Week 12 will be performed based on the per protocol set (PPS) and the efficacy sensitivity analysis set (ESS) using the same analysis methods described in Section 14.2, Section 14.3.3, and Section 14.3.2, respectively.

14.4.3 Remote assessment

Considering the influence of assessment on efficacy evaluation by remote visits (i.e., efficacy endpoints are assessed at non study sites), the analyses of the primary efficacy endpoint IGA response at Week 12, and the secondary endpoints of EASI50, EASI75, and EASI90 at Week 12 will also be evaluated based on the full analysis set (FAS) using the same analysis methods as described in section 14.2, section 14.3 according to different strategies handling remote visit such as treated as missing or imputed (see section 14.4).

14.4.4 Handling of missing data

Missing data will be considered as non-response as described in Section 14.2, Section 14.3, for dichotomous efficacy endpoints. The impact of different imputation methods dealing with missing data such as last observation carried forward (LOCF) will also be further explored based on the full analysis set (FAS) to verify robustness of conclusion.

Last observation carried forward (LOCF): If a patient has no observation at a post-baseline visit (missing), then it will be filled in by last valid observation. Note that only scheduled efficacy assessment results are included in LOCF imputation.

Analysis data sets chosen, rules of handling remote visit assessment and missing data for primary and sensitivity analyses of dichotomous efficacy endpoints are specified in table 8.

Table 8 Summary of analysis for dichotomous efficacy endpoints

	Remote evaluation		Missing data			Prolonged visit		Evaluation endpoint
	Used	Non-response	Deleted	Non-response	LOCF	Deleted	Used	
Primary analysis (FAS)	Y			Y			Y	IGA at week 12, (Method of normal approximation to binomial)
Secondary analysis (FAS)	Y			Y			Y	All dichotomous efficacy endpoints
Sensitivity analysis 1 (PPS)			Y			Y	Y	IGA at week 12, EASI50/75/90 at week 12
Sensitivity analysis 2 (FAS)	Y			Y			Y	IGA at week 12 (exact test)
Sensitivity analysis 3 (FAS)		Y		Y			Y	IGA at week 12, EASI50/75/90 at week 12
Sensitivity analysis 4 (FAS)	Y				Y		Y	IGA at week 12, EASI50/75/90 at week 12
Sensitivity analysis 5 (ESS)			Y	Y			Y	IGA at week 12, EASI50/75/90 at week 12

15.SAFETY ANALYSIS

Safety evaluation will be performed based on SS. Safety evaluation endpoints includes AEs, SAEs, laboratory test results (hematology, blood biochemistry, urinalysis, lipid test, and TSH), vital signs (including blood pressure, pulse, body temperature, and respiratory rate), electrocardiograms, and physical examinations. The duration of medication, total drug exposure information and medication compliance will be summarized.

All safety data will be summarized by treatment group and total.

15.1 STUDY DRUG EXPOSURE AND TREATMENT COMPLIANCE

The total days of actual dosing, total amount of actual dosing and total amount of planned dosing for study drug will be summarized by treatment group using statistics including means, standard

deviation and so on. Proportion of subjects with overdose and omission/interruption will also be provided. Treatment compliance will be calculated based on the administration plan and actual total amount and summarized using statistics including means, standard deviation and so on. The proportion of subjects with treatment compliance < 80%, 80% -120%, and > 120% will be reported, respectively.

The number and percentage of overdoses (i.e., actual daily dose greater than planned), overdoses leading to adverse events (i.e., actual daily dose greater than planned and resulting in clinical signs and symptoms) will also be summarized separately.

The total days of actual dosing, total amount of actual dosing, average amount of actual dosing for study drug and treatment compliance will be derived as follows:

- The total days of actual dosing (days) = (end date 1 - start date 1 + 1) + (end date 2 - start date 2 + 1) +... + (end date of n- start date n + 1), note that only records with actual daily tablets > 0 will be summarized;
- The total amount of actual dosing (tablets) = (end date 1 - start date 1 + 1) * actual daily tablets 1 + (end date 2 - start date 2 + 1) * actual daily tablets 2 +... + (end date n- start date n + 1) * actual daily tablets n;
- The total amount of planned dosing (tablets):
 - If early withdrawal occurs before the end date of the treatment period (i.e., withdrawal before Week 12), The total amount of planned dosing (tablets) = (date of early withdrawal - date of first dose + 1) *2;
 - If not withdrawn or withdrawn after the end date of the treatment period, The total amount of planned dosing (tablets) = min {max (date of last dose - date of first dose + 1, 82), 88} 2;
- Treatment compliance (%) = The total amount of actual dosing (tablets)/ The total amount of planned dosing (tablets).

15.2 ADVERSE EVENTS

According to the Medical Dictionary for Regulatory Activities (MedDRA) (Version 21.0 or later), AEs will be coded using the system organ class (SOC) and preferred terms (PT). Drug related AEs includes "definitely related", "probably related", and "possibly related" AEs. Missing relationship to study drug will be classified as drug-related AEs. The investigator will grade the severity of each adverse event as mild, moderate, and severe. Missing severity will be treated as moderate.

AE will be summarized by SOC and PT. The incidence rate of AE in summary table will be sorted by descending order among SOCs and within a SOC. And the incidence rate is based on the number of subjects with AE(s), not the number of events. If a subject happened more than one same AEs, in the SOC or PT of this AE, only count once for this subject.

AEs during screening phase are defined as any AEs with before the time of start of investigational product administration. Treatment-emergent adverse events (TEAEs) are defined as AEs which commence on or after the time of start of investigational product administration. In the cases where date of AEs is missing or incomplete and it is not possible to define an AE as treatment emergent

or not, the AEs will be classified TEAEs. Serious infections are defined as any infection (viral, bacterial, and fungal) requiring hospitalization or parenteral antimicrobials.

